4.2 OTHER TREATMENTS, EMERGENCY PROCEDURES, RESTRICTIONS

4.2.1 Other treatments and emergency procedures

If a patient is enrolled who is taking an antipsychotic medication that will continue during the treatment period, it is extremely important they continue to take the current antipsychotic medication at the same dose as when the patient was randomized. The dose of an antipsychotic medication can be decreased or discontinued entirely. A patient's dose of antipsychotic medication should be increased only in circumstances of significant worsening of psychosis symptoms that the investigator feels qualifies for a first episode of psychosis. Patients experiencing a first episode of psychosis should continue taking study drug at the discretion of the investigator.

When a patient begins a new prescription or increases their dose of an ongoing antipsychotic medication, this is an outcome event. The available information (e.g., SOPS interview video, medical records from prescribing physician) will be subsequently reviewed by the Central Rating Committee.

Antipsychotic medications will not be provided as part of the clinical trial supplies.

Any change in dose of concomitant antipsychotic medications should be recorded in the source documentation and on the appropriate pages of the eCRF. Prior and concomitant psychotherapy information should also be recorded in the eCRFs.

All patients (i.e., including those on BI 409306 and those on placebo) will receive Brief Supportive Psychoeducation at timepoints described in the [Flow Chart](#). The supportive psychoeducation sessions will be administered by trained site staff and will educate patients and family members about the symptoms of attenuated psychosis syndrome as well as the clinical trial program, risk and protective factors, the impact of stress and the importance of medication adherence. Through these sessions, the patient's and family's needs are evaluated, a symptom reduction plan is developed and referrals for community services may be provided. Refer to Psychoeducation Manual and Materials in ISF.

Any additional treatment that is considered necessary for the patient's welfare may be given at the discretion of the Investigator.

4.2.2 Restrictions

4.2.2.1 Restrictions regarding concomitant treatment

Use of medications known to be strong or moderate CYP1A2 inhibitors is not permitted unless it is documented that the patient is NOT a CYP2C19 poor metabolizer. Patients taking

medication known to be strong or moderate inhibitors of CYP1A2 must be prospectively genotyped to ensure they are not poor metabolizers of CYP2C19.

A patient who is a CYP2C19 poor metabolizer may discontinue use of a strong or moderate CYP1A2 inhibitor medication prior to randomization, at the discretion of the PI.

Use of strong or moderate CYP1A2 inhibitors taken concomitantly with strong or moderate CYP2C19 inhibitors is not permitted. If a patient needs to take strong or moderate CYP1A2 and CYP2C19 inhibitors during the trial for a short period of time (less than 14 days), study drug should temporarily be discontinued.

A list of strong and moderate CYP1A2 and CYP2C19 inhibitors can be found in the ISF.

Use of St. John's Wort is prohibited.

Any medication that may interfere with the action of BI 409306 or whose action may be altered by concomitant administration of BI 409306 during the treatment period and the 4-week follow-up period, in the clinical judgment of the investigator, is not permitted.

4.2.2.2 Restrictions on diet and life style

Because psychoactive drugs may impair thinking, judgment, and/or motor skills, patients will be cautioned about operating machinery, including automobiles, until they are reasonably certain that the study medication does not adversely affect their ability to engage in such activities. It is recommended that patients should exercise caution when driving or operating machinery within two hours of drug administration.

Patients should not abuse alcohol or drugs during the study as defined in the fifth edition of the Diagnostic and Statistical Manual of Mental Disorders (DSM-5), or in the opinion of the investigator. Urine drug screens for amphetamines, cannabis, cocaine, methadone, opiates, and phencyclidine (PCP) will be conducted during the trial for review by the Investigator. Patients with positive drug screens may remain in the trial at the discretion of the investigator.

Patients will be instructed to refrain from caffeine, alcohol, dairy products, and nonprescription medications the evening before and the morning of salivary cortisol sampling. Other than the visits with saliva collection, there are no other restrictions on diet, exercise, or smoking except that the patient's usual habits, including nicotine and caffeine intake, should not be drastically changed.

4.2.2.3 Restrictions regarding women of childbearing potential

Women of childbearing potential must use the contraception methods described in [Section 3.3.2.](#)

4.3 TREATMENT COMPLIANCE

Study medication will be dispensed to the patient at the study site by designated site personnel. Details regarding dispensing of the study medication to each participating patient, including patient identification, the amount of study drug dispensed, the date the drug was dispensed, and the numbers of tablets returned to the site will be recorded in the drug accountability log in the investigator site file.

This trial will utilize a medication adherence monitoring platform (“Platform”). The Platform uses artificial intelligence on smartphones to confirm study medication ingestion. In addition, built-in reminders and a communication system allow real-time intervention in case of drug interruptions.

Use of this Platform will in no way supersede or replace the trial prescribed medication protocol of the patients. Because the Platform does not change the medication protocol of the patients, but rather encourages adherence to the predefined protocol, use of this Platform presents minimal risk to the patients.

The monitoring Platform requires that patients take each dose of the study medication while using a smartphone. The Platform will be provided to a patient preloaded on a smartphone or patients will download the Platform onto their own mobile device.

Patients will receive reminders within predefined time windows to take their medication using the Platform. This notification reminds patients to take their medication dose while using the Platform. Patients will follow a series of prescribed steps in front of the front-facing smartphone camera to visually confirm ingestion of the medication. The application on the smartphone will make an automated determination of whether the patient has properly taken their medication at the prescribed time. There is no need for site staff to review the administration, or be available at the time the patient is taking their medication. The amount of guidance that the device provides to the patient is automatically reduced as the patient becomes more proficient at using the application.

After the device confirms proper study medication ingestion, video recordings will be encrypted and transmitted to a secure centralized location for further analysis, including testing for duplicate enrolment and improving the predictive algorithms, accuracy or usability of the Platform. The captured data and video is reviewable through a roles and rules restricted system ensuring privacy of the information. The system is compliant with the Health Insurance Portability and Accountability Act (HIPAA) in the US, as well as UK and EU data protection regulations, which protect the privacy and security of healthcare information.

Phone numbers of the patients may also be collected and stored in an encrypted manner, allowing for direct communication to each patient from the system in an automated manner, or by site staff or other study monitoring personnel. At no time is the phone number visible. Individuals outside the clinical sites will not be provided with patient names, nor will they be given access to patient medical records.

The Platform will allow for rapid and tailored intervention in case of non-adherence (drug interruptions) without having to visit the clinic for unscheduled visits. Site staff will have access to real-time and continuous adherence data without having to rely on self-reported data. Patients who are found to regularly not take their medication will be contacted by site staff for retraining.

Patients must bring all remaining trial medication including empty package material with them when attending visits. Site staff should remind patients of proper drug administration at each visit during the treatment period. Study medication usage and return must be documented on the respective form and an account must be given for any discrepancies.

Treatment compliance will also be calculated based on tablet counts as the number of tablets taken, divided by the number of tablets which should have been taken according to the scheduled period, multiplied by 100. Compliance will be verified by the on-site monitor authorised by the sponsor.

$$\text{Treatment compliance (\%)} = \frac{\text{Number of tablets actually taken} \times 100}{\text{Number of tablets which should have been taken}}$$

Compliance during the treatment period should be between 80% and 120%. If compliance is outside this range, the patient should be carefully interviewed and re-informed about the purpose and the conduct of the trial. Unreliable patients may be withdrawn from the trial.

The potential for study drug abuse will be closely monitored. Events including overdose, misuse, lost and unaccounted for medication must be thoroughly documented in the patient's source and on the appropriate eCRFs.

5. VARIABLES AND THEIR ASSESSMENT

5.1 TRIAL ENDPOINTS

5.1.1 Primary Endpoint

The primary endpoint is time to remission from APS within a 52 week timeframe.

Per DSM-V, the proposed diagnostic criteria for APS are:

- A. At least one of the following of symptoms is present in attenuated form, with relatively intact reality testing and is of sufficient severity or frequency to warrant clinical attention:
 - Delusions
 - Hallucinations
 - Disorganized speech.
- B. Symptom(s) must have been present at least once per week in the last 1 month
- C. Symptom(s) must have begun or worsened in the past year
- D. Symptom(s) is sufficiently distressing and disabling to the individual to warrant clinical attention
- E. Symptom(s) is not better explained by another mental disorder, including: Depressive or bipolar disorder with psychotic features and is not attributable to physiological effects of a substance or another medical condition
- F. Criteria for any psychotic disorder have never been met.

A diagnosis of APS is defined by the presence of recent attenuated positive symptoms that meet ALL of 5 criteria: sufficient **severity** (criterion A), sufficient **frequency** (criterion B), **recency** of onset or worsening (criterion C), associated with sufficient distress or disability to warrant clinical attention (“**warrant attention** criterion,” criterion D), and not likely due to another disorder (“**attribution** criterion,” criterion E).

A patient in remission is defined as someone who no longer meets the severity criterion.

[figure not shown]
Remission from APS is defined as a score of <3 on all of the P1-P5 Positive Symptom items of the SOPS and maintained until the end of treatment.

5.1.2 Secondary Endpoints

- Time to first episode of psychosis within a 52 week timeframe as adjudicated by the Central Rating Committee. First episode of psychosis defined as one or more SOPS P1-P5 rated a 6 AND either a symptom is seriously disorganized or dangerous OR one of the symptoms above occurred at least one hour per day at an average frequency of four days/week over the past month. OR a new prescription or increase in dose of an ongoing antipsychotic medication. Time of onset of first episode psychosis is defined using the rater's best estimate as determined in the SOPS interview or when

the patient began taking a new prescription or increased the dose of antipsychotic medication.

- Change from baseline in everyday functional capacity as measured by Schizophrenia Cognition Rating Scale (SCoRS) total score after 24 and 52 weeks of treatment.
- Change from baseline in the BAC App composite T score after 52 weeks of treatment.
- Change from baseline in Positive and Negative Syndrome Scale (PANSS) positive items score, negative items score, and total score after 52 weeks of treatment.

5.2 ASSESSMENT OF EFFICACY

Remission of APS, conversion to psychosis, functional capacity, cognitive function, and disease state will be measured by the batteries and questionnaires listed below:

The Structured Interview of Psychosis-Risk Syndromes (SIPS) is a structured interview for diagnosing a clinical high risk (CHR) syndrome for psychosis and cases of first episode psychosis [R16-0681]. It contains a severity rating scale (Scale Of Prodromal Symptoms, or SOPS), a well-anchored Global Assessment of Functioning (GAF) [R16-0594], the DSM-5 schizotypal personality disorder checklist, a brief assessment of the family history of psychosis, the Criteria Of Psychosis-risk Syndromes (COPS) and Presence Of Psychosis Scale (POPS) and DSM-5 Attenuated Psychosis Syndrome criterion sets.

The **SOPS**, contained within the SIPS, assesses Positive, Negative, Disorganization and General symptoms. It is administered as a semi-structured interview with 19 rating scales measuring severity and change of prodromal symptoms. Each item is scored from 0-6. The positive symptoms are scaled from 0 (absent) to 6 (severe and psychotic). The remaining items are scaled from 0 (absent) to 6 (extreme). The 19 rating scales are each independently anchored.

The Positive scale is used to make a diagnosis of attenuated psychosis syndrome (APS) and conversion to psychosis. To meet criteria for APS, a patient must at some point have rated level “3”, “4”, or “5” on at least one of the P1-P5 Positive Symptom items of the SOPS. The symptom(s) must have occurred at the then-current intensity level at an average frequency of at least once per week in the past month, and must not have been likely due to another disorder. The Negative, Disorganization and General domains are used to assess the severity of the diagnosis [\[R15-1441\]](#).

Conversion to psychosis and time to conversion will be adjudicated by the Central Rating Committee after review of video-taped SOPS interview. Adjudication will take into account information provided by patients, informants, and medical records when available.

Schizophrenia Cognition Rating Scale (SCoRS) will be used to evaluate everyday functional capacity.

The SCoRS is a 20-item interview-based assessment of cognitive deficits and the degree to which they affect day-to-day functions. It collects information from a patient interview, interview with an informant (if available), and the administering clinician.

The Schizophrenia Cognition Rating Scale (SCoRS) benefits from receiving information from an informant with frequent contact with the patient. However, it is not required and some patients may wish not to provide contact information for an informant. When conducting the SCoRS, in-person ratings are preferred whenever possible. The informant is any person who interacts with the patient at least 2 times per week.

Each of the 20 items of the SCoRS is rated on a 4-point scale. Higher ratings reflect a greater degree of impairment. The composite score will be the sum of the 20 items [\[R16-4322\]](#).

The Brief Assessment of Cognition in Schizophrenia (BACS) will be used to evaluate cognitive function. There are two versions of the BACS available: the traditional pen-and-paper version and a **tablet based Brief Assessment of Cognition (BAC App)** [\[R17-0578\]](#). The BACS consists of six tests assessing multiple domains of cognitive function: Verbal Memory, Digit Sequencing, Token Motor Task, Semantic and Letter Fluency, Symbol Coding, and Tower of London.

The BAC App will be used for English speaking patients. The BAC App provides digital recording of data, audio recordings of verbally-delivered responses, and examiner-recorded

[figure not shown]
data for post-test verification of responses. Patients who do not speak English will take the pen-and-paper BACS available in their native language.

A composite T score that is calculated using the six standardized scaled sub-test scores will be generated.

Positive and Negative Syndrome Scale (PANSS) will be used to assess the severity of psychotic symptoms and progression of disease. The PANSS positive and negative symptom scales each have 7 items, and the General Psychopathology Scale has 16 items. The patient is rated from 1 to 7 on the 30 different items based on the interview, as well as reports from an informant when possible. The total score is the summation of the 30 item scores [[R13-5061](#)].

The Brief Assessment of Cognition in Schizophrenia: Symbol Coding (BACS SC) and Hopkins Verbal Learning Test-Revised (HVLT-R) will be used to evaluate the effects of BI 409306 on cognitive function, and are variables required for the NAPLS Risk Calculator. The BACS SC measures speed of processing. This timed test involves using a key to write digits that correspond to nonsense symbols. The BACS SC score is the total number of correct responses in 90 seconds.

[figure not shown]
The HVLT-R measures verbal learning. The patient is asked to recall words from a list of 12 words read orally by the Rater. There are three learning trials with each administration. Delayed recall and recognition will not be administered. The HVLT-R score is the total number of words correctly recalled across the three trials.

NAPLS Risk Calculator uses an algorithm designed to predict individualized risk of psychosis in clinical high-risk patients using demographic, clinical, neurocognitive, and psychosocial predictor variables. The web-based risk calculator generates a score representing the probability of transition to psychosis within the next 12 months. The predictor variables used in this study are:

- Age
- Brief Assessment of Cognition in Schizophrenia: Symbol Coding (BACS SC)
- Hopkins Verbal Learning Test-Revised (HVLT-R)
- SIPS items P1 and P2 (unusual thought content and suspiciousness)

- Global Functioning: Social (assessment of decline in social functioning in the past year)

5.3 ASSESSMENT OF SAFETY

Physical examination, vital signs, laboratory tests, ECG, suicidality, extrapyramidal symptoms, and occurrence of (S)AEs will be assessed.

5.3.1 Physical examination

A physical examination will be carried out as described in the [Flow Chart](#).

A physical examination including, but not limited to, general appearance, skin, neck, eyes, ears, nose, throat, breast, lungs, heart, abdomen, back, lymph nodes, extremities, and nervous system will be performed. The physical examination will include examination of known and suspected sites of disease.

Clinically relevant abnormal findings noticed after baseline assessment will be reported as (S)AEs.

5.3.2 Vital Signs

Vital signs (systolic/diastolic blood pressure and pulse rate), height and body weight will be recorded at the study visits as described in the [Flow Chart](#). The same type of instrument/scale should be used for all measurements. Vital signs will be measured after the patient has been sitting for 5 minutes.

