Early D/C Option 1: An EOT Visit must be conducted within 7 days of the last dose of study medication for patients who agree to conduct regularly scheduled visits after premature drug discontinuation. Thereafter, patients should be followed up according to the regular visit schedule for both in-clinic and phone visits. Visit 23 will be the final visit for patients choosing this Early D/C Option.
Early D/C Options 2-4: An EOT Visit must be conducted within 7 days of the last dose of study medication for patients who agree to conduct the remaining visits over the phone, or patients who agree to be contacted or data collected via alternative sources approximately one year after the patient was randomized.
- *** Patients who complete the treatment period will be scheduled for a Follow-Up Visit 28 days after Visit 23. Patients who prematurely discontinue study medication and choose Early D/C Option 1 will not need a Follow-Up Visit. Patients who prematurely discontinue study medication and choose Early D/C Options 2-4 will be scheduled for a Follow-Up Visit 28 days after the EOT visit. See Sections [3.3.4.1](#), [6.2.2](#), and [6.2.3](#).
- **** The End of Study CRFs will be completed at the time of the Follow-Up Visit for completed patients. Patients who prematurely discontinue study drug and remain in the study will have the End of Study CRFs completed one year after randomization.
- 1 Written informed consents/assents for main study and optional pharmacogenomics test for deoxyribonucleic acid (DNA) banking must be obtained before any study-related procedures and assessments are performed. The registration of patients for the study is through the Interactive Response Technology (IRT). Patients who sign the assent and reach the age of majority during the trial must sign the current version of the informed consent. Re-consenting may become necessary when new relevant information becomes available and should be conducted according to the sponsor's and IRB/IEC's instructions.
- 2 Female patients of childbearing potential must perform urine (dipstick) pregnancy test at in-clinic Visits 1 through Visit 23/EOT.
- 3 A 12-lead electrocardiogram (ECG) is to be performed during the scheduled visits or within 24 hours prior to the visit, except for Visit 1 (Screening Visit), where the ECG test will be performed only after a written informed consent/assent for main study has been obtained.

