Only a rapid and short lasting increase in supine pulse rate of 12.5 ± 2.7 beats per minute (bpm) was reported in Chinese CYP2C19 poor metabolizers subjects treated with BI 409306 (100 mg single dose) in study 1289.4. Following this observation, pharmacometric analysis of all available human data revealed a BI 409306 plasma concentration dependent increase in supine pulse rate in typical subjects reaching a maximum of 7-13 bpm (median) at the high exposure end in CYP2C19 poor metabolizers treated with BI 409306 at 100 mg. The maximum effects of BI 409306 on pulse rate were generally achieved at maximum BI 409306 plasma concentrations (20-30 minutes post dose) and disappeared rapidly with declining concentrations [[c01694347-08](#)]. The effects of BI 409306 on pulse rate were further examined in healthy male volunteers under resting and exercise conditions following single oral doses of 50 and 200 mg [[c03808525-01](#)]. In line with previous results, heart rate profiles closely correlated with drug systemic exposure profiles and the heart rate increase was 11.51 bpm at the maximum individual plasma concentration measured during exercise.

Altogether, good to satisfactory safety and tolerability were observed in single doses of BI 409306 (up to 350 mg in CYP2C19 extensive metabolizers (EM); up to 100 mg in CYP2C19 poor metabolizers (PM)) in healthy young volunteers and multiple doses (14 days up to 100 mg EM/50 mg PM) of BI 409306 in healthy young and elderly subjects. In addition data from completed studies demonstrate that the increase in heart rate was transient, closely related to the time of maximum drug concentrations, and of low amplitude [[c01694347-08](#)].

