2.3 BENEFIT - RISK ASSESSMENT

Overall, BI 409306 shows a favorable nonclinical safety profile. There was no genotoxic potential of BI 409306. The toxicological profile of BI 409306 is characterized by cardiac effects which seem to be consistent with those described for phosphodiesterase inhibitors in general. Previous clinical trials found that BI 409306 was well tolerated in young and elderly healthy subjects in single doses of 0.5 to 350 mg and multiple doses up to 100 mg once daily. Data from the recently completed 1289.6 trial in 518 subjects with schizophrenia demonstrated AEs for 10 mg, 25 mg and 50 mg to be in the range of placebo. The most frequent drug related adverse events reported in all trials were visual side effects that occurred shortly after dosing and mostly resolved within 1 hour [[c09991178-01](#)]. A dedicated ocular safety study demonstrated no relevant changes to ocular parameters [[c09168615-01](#)] and a dedicated cardiovascular safety study found exercise testing did not suggest a clinically relevant impact on heart rate or cardiac function. All adverse effects generally were restricted to high dose levels and were reversible [[U12-1034](#); [U13-1182](#); [U12-2165](#); [U13-1303](#)]. Cardiac function will be monitored during the study according to the [Flow Chart](#).

It is expected that the metabolic clearance of BI 409306 will be similar for adolescents and adults. Any possible effects on sexual maturation will be monitored clinically via appropriate endocrine markers. Inclusion of adolescents in this trial is based on the recognition that the clinically high-risk state is already apparent in these adolescents and the criteria and symptomatology in adolescents under 18 is identical to the presentation of the older individuals.

As with all drugs, the potential for hypersensitivity and allergic reactions have to be taken into consideration when BI 409306 is administered. Other risks are inherent to any clinical trial such as unexpected adverse clinical or laboratory events. Although rare, a potential for drug-induced liver injury (DILI) is under constant surveillance by sponsors and regulators. Therefore, this trial requires timely detection, evaluation, and follow-up of laboratory alterations in selected liver laboratory parameters to ensure patients' safety, see also [Section 5.3.6.1](#).

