7.8.3 Vital signs

Only descriptive statistics are planned for this section of the report. See **section 7.3.4** of the CTP.

[figure not shown]

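### Pulse and ECG readings are not tied to time of dosing, so as summarised they can neither show nor exclude the short post-dose heart-rate effect that the protocol describes

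*Protocol*

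**What the plan says.** Protocol 1.2 gives the timing of the known effect: "The maximum effects of BI 409306 on pulse rate were generally achieved at maximum BI 409306 plasma concentrations (20-30 minutes post dose"). It adds that the effects "disappeared rapidly with declining concentrations". The largest figure there is a median of 7-13 bpm at the high-exposure end, in CYP2C19 poor metabolizers given 100 mg. A separate single-dose study (50 and 200 mg, healthy men) found 11.51 bpm at maximum individual concentration during exercise.

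Protocol 2.3 relies on the schedule as a safeguard: "Cardiac function will be monitored during the study according to the" Flow Chart.

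The measurement rules are:

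- Vital signs (5.3.2): "Vital signs will be measured after the patient has been sitting for 5 minutes".
- ECG (5.3.4): after five minutes supine. Flow Chart footnote 3 says that it "is to be performed during the scheduled visits or within 24 hours prior to the visit".
- Visit 2: footnote 17 puts the first dose after all baseline assessments, so those readings are pre-dose.
- Dosing (4.1.4): morning and evening, about 12 hours apart.

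On analysis, Protocol 7.3.4 is descriptive with no hypothesis testing. SAP 7.8.3 says of vital signs: "Only descriptive statistics are planned for this section of the report". SAP 7.8.4 handles clinically significant new ECG findings as adverse events. SAP 6.7 takes Visit 1 as baseline for both. None of these sections uses time since dose.

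**The concern.** The protocol knows when the heart-rate effect occurs, but the schedule does not place readings at that time or ask when they were taken relative to a dose. A seated pulse 25 minutes after a tablet and one 10 hours after it go into the same summary, and only the first says anything about the peak.

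Three features make this more than a formality. Section 2.3 counts the scheduled cardiac monitoring among the safeguards. CYP2C19 poor metabolizers, the group with the largest reported effect, are excluded only if they also take a strong or moderate CYP1A2 inhibitor (exclusion 16), and screening genotyping covers only patients on such inhibitors (5.5.2). Some may therefore be enrolled unidentified at screening. And the protocol does control timing elsewhere: time of day for saliva and biomarker samples (footnote 6), and within 60 minutes for the cognitive tests (6.2).

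At stake is what the 52-week pulse data can be said to show. A small difference between arms would be compatible both with no post-dose effect and with one that was rarely sampled.

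**Working it through.** The plan states no figure on this point, so there is none to reproduce. The check is a reading of the text followed by an illustration of scale.

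**Text.** I looked for a time-after-dose rule, a request to record time since dose, or an analysis by it in the Flow Chart footnotes, Protocol 1.2, 2.3, 4.1.4, 4.3, 5.3.2, 5.3.4 and 7.3.4, and SAP 6.7, 7.8.3 and 7.8.4. None appears in the readable text. The only dose scheduled in clinic is on Day 1, with no later reading scheduled that day. The 24-hour ECG allowance spans two dosing intervals.

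**Share of the dosing interval** (12 h = 720 min, from 4.1.4):

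- 20-30 minutes after dose: 10/720 = 1.4%
- first hour: 60/720 = 8.3%
- first two hours: 120/720 = 16.7%

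**Illustrative dilution.** Taken from the documents: peak at 20-30 min (midpoint tp = 25/60 = 0.417 h) and the 12 h interval. Assumed: linear rise to tp, exponential decline with half-life h, and readings uniform over the interval. The documents give no effect duration or half-life and no distribution of visit times.

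Mean fraction of peak = [tp/2 + (h/ln 2) × (1 − 2^(−(12 − tp)/h))] / 12

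| h (assumed) | Calculation | Fraction of peak | If peak 7 bpm | If peak 13 bpm |
|---|---|---|---|---|
| 0.5 h | (0.208 + 0.721)/12 | 0.078 | 0.5 | 1.0 |
| 1 h | (0.208 + 1.442)/12 | 0.138 | 1.0 | 1.8 |
| 2 h | (0.208 + 2.833)/12 | 0.253 | 1.8 | 3.3 |
| 3 h | (0.208 + 4.030)/12 | 0.353 | 2.5 | 4.6 |

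The fraction does not depend on the size of the peak. The bpm columns use the poor-metabolizer, 100 mg figures only for scale.

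**Sensitivity to visit timing.** If all readings fell 2-6 h after a dose, the fraction would be 0.02, 0.11, 0.31 and 0.45 for the same four half-lives. The range moves with an assumption that the documents cannot settle, and recording the times would settle it.

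**The case against.** The strongest reply is that this trial is not where the peak effect is studied. Protocol 1.2 reports a pharmacometric analysis of all available human data and a dedicated rest-and-exercise study. Section 2.3 says that exercise testing did not suggest a clinically relevant impact. The protocol calls the effect transient and of low amplitude. Routine visits can look for sustained change, and clinically relevant findings go to adverse-event reporting. That stands: not repeating a peak-effect study in a phase II efficacy trial is defensible. It does not make untimed readings informative about the peak, and the dedicated study used single doses in healthy men.

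A reader might infer several stronger points that the documents do not support:

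- *That the trial will conclude there is no cardiac effect.* No such conclusion is planned, and the protocol itself says that the effect exists.
- *That 7-13 bpm is the effect at stake here.* That figure is for poor metabolizers at 100 mg. The trial gives 50 mg b.i.d., and the typical effect may be smaller.
- *That the same dilution applies to the ECG.* SAP 7.8.4 plans no comparison of ECG means.
- *That blood pressure peaks at the same time.* No peak time is given for it.
- *That clock times are not collected.* The eCRF is not in the documents and parts of both documents are redacted. What can be said is that the readable text does not ask for them.

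It is also fair that bins by time since dose may be sparse. SAP section 4 says that the sample is much smaller than intended.

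**Conclusion.** The point holds for pulse rate and, as a matter of recording, for ECG heart rate. As written, the readings can detect sustained changes and clinically relevant abnormalities. They cannot show or exclude the short post-dose heart-rate effect.

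The text comparison is firm. The size is not: 8-35% of peak rests on uniform timing over 12 hours and an assumed half-life of 0.5-3 hours, and other visit timing moves it. It is also tempting to state as fact that most readings miss the effect. The documents give neither the effect's duration nor the visit times, so that remains a likely consequence under assumptions. This is a cheap improvement to what the pulse data can support, and does not show that the safety monitoring as a whole is inadequate.

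**What to change.** - **Protocol 5.3.2 and 5.3.4:** record the clock time of each pulse and ECG reading and the time of the last dose. Section 4.3 says: "The monitoring Platform requires that patients take each dose of the study medication while using a smartphone". Dose times may therefore be available from the Platform, but the documents do not say that it exports them. If it does not, ask at the visit.
- **SAP 7.8.3:** add one descriptive table of pulse rate by arm and time since last dose, for example 0-2 h, >2-6 h and >6 h. Include ECG heart rate if it is captured. Blood pressure may be tabulated the same way, with a note that no peak time is documented for it.
- **SAP text:** state that readings outside the early post-dose window do not assess the peak effect. If data collection is too far advanced to add fields, this sentence is the minimum.

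The cost is one or two time fields, a possible merge with Platform data and one extra table, with no added visit or procedure. The downside is a possibly sparse 0-2 h cell. The table would then document the limitation and would not measure the effect.
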